**Figure 2-2 Study design Part 1**

Study Day	1	7	14	21	28	29	56	84
Study visit ↑	↑	↑	↑	↑	↑	↑	↑	↑
Screening BL	<	4 week treatment period				Follow up EOS		

BL = Baseline assessments

EOS = End of Study visit

↑ = Study visit ↑ = Optional study visit

Patients will be asked to arrive at the study site approximately 2 hours prior to dosing on Day 1. Patients in Cohort 1 will be randomized in a 2:1 ratio to receive the starting dose of 0.03 mg LJN452 or placebo. Safety assessments will be performed for 4 hours post dose and pharmacokinetic [REDACTED] assessments will be performed for up to 8 hours post first dose. Prior to discharge, the patients will be given a supply of LJN452 or placebo and instructed to take first thing in the morning with water, prior to eating every day.

Patients will then return on Days 7, 14 and 21 for safety, pharmacokinetic [REDACTED] assessments and dosing. Patients will be asked to return to the study site on Day 28, for the final dosing visit, when safety, pharmacokinetic [REDACTED] assessments will be performed. Patients will be asked to return to the study site for an optional ambulatory visit on Day 29, where 24 hour post dose pharmacokinetic [REDACTED] assessments will be performed.

[figure not shown]
Patients are asked to return to the study site on approximately Day 56 for follow up assessments. An end of study visit will take place at approximately Day 84.

A dose escalation review and an interim analysis are planned when at least 12 patients have completed dosing and Day 28 assessments in Cohort 1. The main purpose of the interim analysis will be to evaluate the observed variability in GGT levels and, if needed, consider a sample size re-estimation.

Additional cohorts will follow the same schedule as Cohort 1. Further cohorts may be added depending on emerging safety and PK/PD data. Additional interim analyses may be performed after a minimum of 12 patients in each cohort finish dosing and Day 28 assessment. The sponsor will be unblinded and the Clinical Trial Team may be unblinded when all subjects in a cohort have completed 28 day of study hence at the time of the planned IAs.

**Part 2**

Approximately 88 patients with PBC, with an incomplete biochemical response to, but still taking, UDCA or those not currently taking UDCA are planned to be recruited into Part 2, with the aim that 80 will complete the study. Patients who participated in Part 1 may be recruited to Part 2, provided they meet all required eligibility criteria and have not received study medication within 3 months of Randomization (or longer if required by local regulations).

**Figure 2-3 Study design Part 2**

BL = Baseline assessments (performed pre-dose Day 1)

↑ = Study visit

TC = Telephone Contact

EOS = End of Study visit

A screening visit will take place, where patient's eligibility to enter the study will be assessed.

Eligible patients will be asked to arrive at the study site approximately 2 hours prior to dosing on Day 1 to perform Baseline assessments.

Patients will be randomized in a 3:3:2 ratio to receive either LJN452 Dose level 1, LJN452 Dose level 2 or placebo. Following drug administration, safety, pharmacokinetic [REDACTED] assessments will be performed at 2 hours post dose.

Prior to discharge, the patients will be given a supply of LJN452 or placebo and instructed to take their dose first thing in the morning with water, prior to eating every day.

Patients will then return at weeks 3, 5, 9 and 13 for safety, tolerability, pharmacokinetic [REDACTED] assessments. A telephone contact will be made one week after start of dosing to check their progress and check they have no questions.

Patients will be asked to return to the study site in week 17 for follow up assessments and to complete their end of study assessments.

### 3 First interpretable results (FIR)

First interpretable results (FIR) will be provided for this trial.

The study FIR template (mock slides) can be found in CREDI in the study RAP folder.

The template shows the analysis / results to be presented in the FIR. Study outputs required to be created at the time of the FIR will be highlighted in TFL shells document and marked as "Key" in the Programming Deliverables Tracker (PDT) output list.

### 4 Interim analyses

The first interim analysis will be performed when at least 12 patients in Cohort 1 have completed 4 weeks of dosing at 0.03 mg and Day 28 post dose assessments. The purpose of this interim analysis is to assess patient safety, to evaluate the assumption on intra-subject variability of GGT, which was used for sample size calculations, and to select a dose for the next cohort. An ANCOVA model will be fitted to estimate the change from baseline in GGT and its variability, and an unblinded sample size re-estimation conducted. The results may be used to adjust the size of the next cohort.

Doses in subsequent cohorts of Part 1 will be decided based on accumulated information collected from all previous cohorts including safety, PK and PD data.

Additional interim analyses will be performed when at least 12 patients in subsequent cohorts of Part 1 have completed 4 weeks of dosing and Day 28 assessments. Placebo data from all cohorts will be pooled in the ANCOVA model to evaluate the treatment difference between each dose level of LJN452 versus placebo. The model described in the primary analysis section will be fitted, as it is indeed the same analysis which will be included in the final study report.

Results from Part 1 will be used to select the doses for Part 2, which may be initiated prior to the completion of Part 1. Part 2 will not be initiated if the estimated change from baseline in GGT at Day 28 is smaller than 20% at the highest dose level of LJN452 in Part 1.

Unblinded interim analysis results from Part 1 will be reviewed by an internal Novartis Interim Analysis Team which may include some CTT members. The Interim Analysis Team may communicate interim results to relevant Novartis teams for information, consulting and/or decision purposes. The composition of the interim analysis team will be decided before the FPFV and a roster of membership maintained in the trial master file.

The Interim Analysis Team may communicate interim results (e.g., evaluation of PoC criteria or information needed for planning/modifying another study) to relevant Novartis teams for information, consulting and/or decision purposes.

No further dissemination of interim results based on un-locked data should occur, in particular not with individuals involved in treating the study's subjects or assessing clinical data (e.g., ECGs, images, symptoms) obtained in the study.

In Part 2 of the study, an interim analysis is planned when approximately 40 patients have completed their Week 8 visit. The purpose of this interim analysis is to review the sample size (calculated based on GGT and ALP changes) to assess if it is also adequate to provide precise enough treatment difference estimates in itch parameters, a key tolerability endpoint. A blinded sample size re-estimation will be performed and a proposal to increase the sample size submitted to the DMC as needed. The DMC will decide whether it is appropriate to increase the sample size based on an unblinded interim analysis, which will be performed by a study independent statistician and programmer with outputs provided to the DMC only. Recruitment will continue while the IA is being performed.

This study will utilize a staggered lock of the clinical database, so that the data can be locked after completion of Part 1, or a set of Cohorts in Part 1.

Once a Cohort's data has been locked, treatment codes for the relevant cohort(s) will be released and made available for data analysis.

The results from the locked Part 1 interim analysis can be communicated beyond Novartis to groups including, but not limited to individuals treating the study's subjects, health Authorities and reported on clinical registries.

Additional interim analyses [REDACTED] may be conducted to support decision making concerning the current clinical study, the sponsor's clinical development projects in general or in case of any safety concerns.

No dose escalation is planned in Part 2.

## DMC

In Part 2, in addition to frequent review of the emerging study data by the study team, the DMC will review safety, including AEs and laboratory parameters, on a regular basis. In addition, in the event that more than 3 patients develop an AE of CTCAE Grade 3 or higher in the same system organ class, the DMC Chair will be alerted and may call an *ad hoc* DMC meeting. Further details regarding relevant data and actions will be specified in the separate DMC charter. The DMC may call for the study to be placed on hold to further enrollment, and the study may be stopped based on a full review of all available clinical safety data.

The DMC charter contains specific details and outputs for the DMC are contained in a separate document.

## 5 Statistical methods: Analysis sets

For all analysis sets, subjects will be analyzed according to the study treatment(s) received. Subjects with dose reduction due to ALT/AST will be analyzed according to the treatment they received up to the dose reduction in Part 2.

The safety analysis set will include all subjects that received any study drug and experienced no protocol deviations with relevant impact on safety data.

The PK analysis set will include all subjects with at least one available valid (i.e., not flagged for exclusion) PK concentration measurement, who received any study drug and experienced no protocol deviations with relevant impact on PK data.

The PD analysis set will include all subjects with available PD data and no protocol deviations with relevant impact on PD data.

The analysis sets and protocol deviation codes are related as follows:

**Table 5-1 Protocol deviation codes and analysis sets**

Category Deviation code	Text description of deviation	Data exclusion
Subjects are excluded from all (safety) analysis in case of these PDs:		
I01	ICF not obtained	Yes
S02	Subject did not receive any study drug	Yes
Subjects are excluded from PK analysis in case of these PDs:		
I01	ICF not obtained	Yes
S02	Subject did not receive any study drug	Yes
Subjects are excluded from PD analysis in case of these PDs:		
I01	ICF not obtained	Yes
S02	Subject did not receive any study drug	Yes

Category Deviation code	Text description of deviation	Data exclusion
I03	Diagnosis of PBC not demonstrated	Yes
I07 (Part 1)	Additional inclusion criterion for Part 1 not met	Yes
I08 (Part 2)	Additional inclusion criterion for Part 2 not met	Yes
D01	Withdrawal criteria met but subject not discontinued	Yes
Subjects are excluded from PK and PD analysis in case of these PDs:		Exclude subject from PK and PD analysis sets
I01	ICF not obtained	Yes
S02	Subject did not receive any study drug	Yes
I03	Diagnosis of PBC not demonstrated	Yes
I07 (Part 1)	Additional inclusion criterion for Part 1 not met	Yes
I08 (Part 2)	Additional inclusion criterion for Part 2 not met	Yes
D01	Withdrawal criteria met but subject not discontinued	Yes

If updates to this table are needed, an amendment to RAP M3 needs to be implemented prior to DBL.

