7.1 Discontinuation of study treatment

Discontinuation of study treatment for a subject occurs when study treatment is stopped earlier than the protocol planned duration. Discontinuation of study treatment can be decided by either the subject or the investigator.

Study treatment **must** be discontinued under the following circumstances:

- Subject decision - subjects may choose to discontinue study treatment for any reason at any time.
- The investigator believes that continuation would negatively impact the safety of the subject or the risk/benefit ratio of trial participation.

- Pregnancy.
- Hypersensitivity reaction to LJN452.
- Hepatic decompensation event such as variceal bleed, uncontrolled ascites, encephalopathy, spontaneous bacterial peritonitis.
- A Liver or Renal event indicating discontinuation as defined in [Table 15-1](#) - Follow up requirements for Liver events or [Table 15-2](#) - Follow up requirements for renal events
- An AE with a CTCAE rating of Grade 3 that are suspected to be related to study drug (apart from pruritus, liver or renal parameters, see [Table 15-1](#), [Table 15-2](#) and [Table 16-1](#) for required actions).
- An AE with a CTCAE rating of Grade 4 or higher, regardless of attribution to study drug
- Emergence of the following adverse events: Diarrhea, nausea, vomiting, recurrent positive fecal occult blood or other GI symptoms that are deemed to be intolerable.

The appropriate personnel from the study site and Novartis will assess whether study treatment should be discontinued for any subject whose treatment code has been broken inadvertently for any reason.

If discontinuation of study treatment occurs, the investigator must determine the primary reason for the subject's premature discontinuation of study treatment and record this information on the Dosage Administration CRF.

After study treatment discontinuation, at a minimum, in abbreviated visits, the following data should be collected at clinic visits or via telephone/email contact:

- new / concomitant treatments
- adverse events/Serious Adverse Events

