11.1 Analysis sets

For all analysis sets, subjects will be analyzed according to the study treatment(s) received. Subjects with dose reduction due to ALT/AST will be analyzed according to the treatment they received up to the dose reduction in Part 2.

The safety analysis set will include all subjects that received any study drug.

The PK analysis set will include all subjects with at least one available valid (i.e., not flagged for exclusion) PK concentration measurement, who received any study drug and experienced no protocol deviations with relevant impact on PK data.

The PD analysis set will include all subjects with available PD data and no protocol deviations with relevant impact on PD data.

Details of protocol deviations which warrant exclusion from either the PK or PD analyses data sets will be provided in the RAP document Module 3.

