### 1.2 Changes to RAP documentation (M3)

Refer to corresponding guidances and NIBR RAP Addendum template for detailed information on the requirements of documenting changes to RAP documentation.

**For the statistical methodology (M3),** any major changes to the statistical methodology should be reflected in the RAP M3 documentation via version control (M3 amendment) (new document version to be approved by the trial team as the original module).

Such major changes could include (but are not limited to):

- change in statistical methodology
- substantial change in (derivation of) main endpoint
- substantial change in study design (e.g. protocol amendment introducing new multiple-dose cohorts in a so far single-dose trial)

Such changes may also require a protocol amendment to ensure consistency. In addition they need to be mentioned (high-level) in the CSR (section for changes to planned analysis).

Minor changes to the RAP M3 documentation can be captured e.g. by a study note to file / note in RAP Addendum or within the CSR itself.

Corrections of typographical errors or modification of spelling (from English to American, for example) do not need to be incorporated into the RAP M3 documentation.

This RAP M3 Amendment 1 is to reflect the following changes:

- The addition of a deviation code leading to exclusion from the PD analysis set in Table 5-1.
- The addition of the time by log-transformed baseline term in the repeated measures analysis model in Section 7.1.3.
- The changes to the study design in protocol amendment 5.

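### SAP Table 5-1 drops whole subjects from the only set used to model GGT and ALP because of a post-randomisation conduct deviation (D01); the bias is probably small and the fix is cheap

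*SAP*

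**What the plan says.** SAP section 5 defines three sets: safety, PK and PD. On the last it says: "The PD analysis set will include all subjects with available PD data and no protocol deviations with relevant impact on PD data". Table 5-1 then lists the deviation codes. D01, "Withdrawal criteria met but subject not discontinued", appears in the PD block and again in the block headed "Subjects are excluded from PK and PD analysis in case of these PDs". In both, the exclusion applies to the subject, not to records after the deviation. D01 is not in the safety block.

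The GGT model (SAP 7.1.3) and the ALP model (SAP 7.2.3, same approach) stand in SAP section 7, on PD parameters. Section 7.1.3 does not name its analysis set, but the PD set is the only defined one that fits.

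Protocol 7.1 lists when study treatment must stop. The list includes "An AE with a CTCAE rating of Grade 3 that are suspected to be related to study drug" (with pruritus, liver and renal parameters handled separately) and "A Liver or Renal event indicating discontinuation as defined in" the appendix tables. It also has criteria with no drug link, such as pregnancy. Subjects who stop treatment are not counted as withdrawn unless they withdraw consent, and are asked to come back for follow-up where possible.

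The exclusion list is left to the SAP. Protocol 11.1 says: "Details of protocol deviations which warrant exclusion from either the PK or PD analyses data sets will be provided in the RAP document", Module 3. The note under Table 5-1 gives the route for changes: "If updates to this table are needed, an amendment to RAP M3 needs to be implemented prior to DBL".

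**The concern.** The other codes specific to the PD set (I03, I07, I08) are eligibility failures fixed at entry. D01 is different in kind: it can only arise on study, and it needs two things together, a criterion being met and the site not acting on it. Take two subjects with the same suspected drug-related event. The one stopped correctly stays in the PD set. The one not stopped is removed, along with every valid visit before the event.

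If D01 occurs unequally across arms, and D01 subjects differ from the others in GGT or ALP change, the fold change versus placebo is biased. The sign depends on which subjects are lost, so it cannot be stated in advance.

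No other planned model repairs this. The additional analyses change the handling of values after a dose reduction, the pooling of the two parts, or the covariance matrix; none changes the set. D01 subjects remain visible in the safety laboratory summaries, but only descriptively.

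Blinding helps in part. In Part 2 the sponsor stays blinded and deviations are determined before treatment codes are released (protocol 6.4 and 10.2). That limits coding informed by treatment, but not unequal occurrence. In Part 1 the sponsor is unblinded at each cohort's interim analysis, so the protection is weaker there.

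**Working it through.** **Inputs from the documents**
- Part 2: 30 evaluable per active dose, 20 on placebo (protocol 11.6, 11.7).
- ALP: difference 15 points, SD 17.8, two-sided 5% t-test, stated power 81% (protocol 11.7).
- GGT: difference 0.50, SD 0.28 (protocol 11.6).
- Part 1: 10 per dose arm and 5 placebo per cohort (protocol 6.2). With 2 to 5 cohorts, pooled placebo is 10 to 25.
- Planned output: two-sided 90% confidence intervals (SAP 7.1.3).

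**Planning figures reproduced (noncentral t)**
- ALP: SE = 17.8 × √(1/30 + 1/20) = 5.14; 15/5.14 = 2.92; 48 df; power 81.6% (stated 81%).
- GGT Part 1, 8 vs 4, 90% interval: SE = 0.28 × √(1/8 + 1/4) = 0.1715; 0.50/0.1715 = 2.92; 10 df; 85.7% (stated about 85%).
- GGT Part 2: above 99.9% (stated at least 95%).

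**Bias formula**

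If k of n subjects in an arm are excluded, and they differ from the retained subjects by d SD, the retained mean differs from the full-arm mean by (k/n) × d SD. For active versus placebo:

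bias (SD units) = (k₁/n₁ − k₀/n₀) × d

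Multiply by 17.8 for ALP points and by 28 for GGT points. Error rates are for a two-sample t-test on the retained subjects when the true full-arm difference is zero.

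**Scenarios (assumed; the documents give no D01 rate), d = 0.25 / 0.5 / 1.0**

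| Excluded, active vs placebo | Bias, SD | ALP points | GGT points | Two-sided 5% test, % | 90% CI excludes 0, % |
|---|---|---|---|---|---|
| 1/30 vs 0/20 | 0.008 / 0.017 / 0.033 | 0.15 / 0.30 / 0.59 | 0.23 / 0.47 / 0.93 | 5.01 / 5.04 / 5.14 | 10.01 / 10.05 / 10.22 |
| 3/30 vs 0/20 | 0.025 / 0.05 / 0.10 | 0.45 / 0.89 / 1.78 | 0.70 / 1.40 / 2.80 | 5.08 / 5.32 / 6.27 | 10.12 / 10.47 / 11.89 |
| 3/30 vs 1/20 | 0.0125 / 0.025 / 0.05 | 0.22 / 0.45 / 0.89 | 0.35 / 0.70 / 1.40 | 5.02 / 5.08 / 5.31 | 10.03 / 10.11 / 10.46 |
| 3/30 vs 2/20 | 0 | 0 | 0 | 5.00 | 10.00 |

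Worked case, 3/30 vs 0/20 at d = 1: bias = 0.10 SD. SE on 27 vs 20 = √(1/27 + 1/20) = 0.295 SD. The shift is 0.10/0.295 = 0.34 SE.

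Stress case, 3/30 vs 0/20 at d = 2: ALP 0.20 × 17.8 = 3.6 points, GGT 0.20 × 28 = 5.6 points, and the 5% test rejects about 10% of the time.

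**Part 1, GGT, 1 of 10 in one dose arm, none on placebo**
- Bias 0.70 / 1.40 / 2.80 points against 50.
- 90% interval error 10.05 / 10.19 / 10.74% with 10 pooled placebo, and 10.07 / 10.27 / 11.07% with 25.
- On the 8 evaluable active patients of the planning calculation, 1/8 at 1 SD gives 28/8 = 3.5 points.

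**Information lost**
- ALP power: 81.6% at 30/20, 81.0% at 29/20, 79.8% at 27/20.
- Each excluded Part 2 subject removes up to four post-baseline GGT and ALP values (weeks 3, 5, 9 and 13), including valid ones.

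These figures are on the planning scale. The actual model uses log change with a baseline covariate, so they show order of size only.

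**The case against.** The strongest objection is that this hardly matters. The upper figures need three violations, all in one active arm, none on placebo, each differing by 1 SD; if D01 is balanced in rate and kind, the bias is zero. The study is exploratory, reports 90% intervals and makes no multiplicity adjustment. All of that stands, and it is why this is a cheap improvement and not a threat to the trial. It does not make the exclusion sound.

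Second, D01 is undefined and its programming may be specified in Module 8, which is not available here. The word withdrawal could also reach consent withdrawal. So the link to treatment rests on an assumed reading, though the point that D01 arises after randomisation does not. If consent was withdrawn, protocol 7.3 governs what may be used, whatever the analysis set.

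Third, keeping D01 subjects brings in values recorded after a withdrawal criterion was met, and correctly stopped subjects may have few later laboratory values, because GGT and ALP are not in the post-discontinuation minimum of protocol 7.1. The two groups will not be fully alike. This is a real cost. The values are nonetheless observed under the subject's study treatment, and the supportive run without D01 subjects shows how much they weigh.

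Finally, protocol section 13 already requires significant deviations to be reported in the CSR. That documents the cases but does not return them to the model.

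**Conclusion.** The concern holds. Table 5-1 makes inclusion in the primary GGT and secondary ALP comparisons depend on a post-randomisation event and on the site's handling of it, and no planned model includes the subjects removed.

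The effect is probably small. Within the main Part 2 scenarios the bias is at most 0.10 SD, about 12% of the planned ALP difference (1.78/15) and 6% of the GGT difference (2.8/50). The judgement is less secure for ALP than for GGT, in the small Part 1 arms (one case is 10% of a dose arm of 10), and if cases cluster in one dose arm.

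It rests on an assumed D01 rate, an assumed difference between excluded and retained subjects, and reading D01 as referring to protocol 7.1. The direction is unknown.

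**What to change.** By RAP M3 amendment before database lock:

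- Delete D01 from the PD block and from the combined PK-and-PD block of Table 5-1. The second deletion also removes D01 as a PK exclusion, which agrees with the separate PK block.
- Leave I01, S02, I03, I07, I08 and the as-treated rule unchanged. The SAP 7.1.3 rule on data after a dose reduction also stays and applies to D01 subjects as to others, so a D01 subject with a reduction regains only the earlier visits under it.
- Keep D01 subjects' observed values in the primary GGT model, the ALP model and the itch analyses.
- Re-run the GGT and ALP models without D01 subjects as a supportive analysis, and report D01 counts by part and arm.

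The cost is one SAP amendment and one extra run of each model, with no additional patients. No protocol amendment is needed, because protocol 11.1 leaves the list to RAP Module 3. The same route has been used before: SAP 1.2 records "The addition of a deviation code leading to exclusion from the PD analysis set in Table 5-1", without naming the code.

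A separate editorial point: the PK block (two codes) and the combined block (six codes) imply different PK sets and should be reconciled.
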